**9.7.6.1 Adverse Events**

AEs will be coded by system organ class (SOC) and preferred term using the *Medical Dictionary for Regulatory Activities*.

An AE (classified by preferred term) that occurs during the OLTP or thereafter will be considered a treatment-emergent adverse event (TEAE) if it was not present before the date of the first dose of IP in the OLTP or was present before the first dose of IP in the OLTP and increased in severity during the OLTP or thereafter. If more than 1 AE is reported before the date of the first dose of IP in the OLTP and coded to the same preferred term, the AE with the greatest severity will be used as the benchmark for comparison with the AEs occurring during the OLTP that were also coded to that preferred term.

An AE (classified by preferred term) that occurs during the DBTP of the study will be considered a newly emergent adverse event (NEAE) if the AE was not present before the first dose of the double-blind IP or it was present before the first dose of the double-blind IP and increased in severity during the DBTP. If more than 1 AE is reported before the first dose of the double-blind IP and coded to the same preferred term, the AE with the greatest severity will be used as the benchmark for comparison with the AEs occurring during the DBTP that were also coded to that preferred term. An AE that occurs more than 30 days after the date of the last dose of IP will not be counted as a NEAE.

The number and percentage of patients reporting TEAEs during the OLTP will be tabulated by SOC and preferred term. Similarly, the number and percentage of patients reporting NAEs during the DBTP will be tabulated by SOC and preferred term. The number and percentage of patients in each treatment group reporting TEAEs and NAEs during the DBTP will be tabulated by SOC and preferred term; by SOC, preferred term, and severity; and by SOC, preferred term, and causal relationship to the IP. If more than 1 AE is coded to the same preferred term for the same patient during the same treatment period, the patient will be counted only once for that preferred term using the most severe and most related occurrence for the summarization by severity and by causal relationship to the IP.

The distribution of TEAEs and NAEs by severity and relationship to the IP will be summarized for each treatment group for the DBTP.

The incidence of common ( $\geq 2\%$  of patients in any treatment group) TEAEs and NAEs during the DBTP will be summarized by preferred term and treatment group and will be sorted by decreasing frequency for the weekly rapastinel group.

An SAE that occurred between the date of the first dose of the open-label IP and 30 days after the date of the last dose of double-blind IP, inclusive, will be considered an on-therapy SAE. The number and percentage of patients who had on-therapy SAEs during the OLTP will be summarized by preferred term and sorted by decreasing frequency. The number and percentage of patients who had on-therapy SAEs during the DBTP will be summarized by treatment group and preferred term and will be sorted by decreasing frequency for the weekly rapastinel group.

The number and percentage of patients who had fatal on-therapy SAEs during the OLTP will be summarized by preferred term and sorted by decreasing frequency. The number and percentage of patients who had fatal on-therapy SAEs during the DBTP will be summarized by treatment group and preferred term and sorted by decreasing frequency for the weekly rapastinel group.

The incidence of TEAEs leading to premature discontinuation of IP during the OLTP will be summarized by preferred term and will be sorted by decreasing frequency. The incidence of TEAEs and NAEs leading to premature discontinuation of IP during the DBTP will be summarized by preferred term and treatment group and will be sorted by decreasing frequency for the weekly rapastinel group.

Listings will be presented for all patients with SAEs, patients with AEs leading to discontinuation, and patients who died (if any).

[REDACTED]

[REDACTED]

[REDACTED]

[REDACTED]

[REDACTED]

[REDACTED]

[REDACTED]

[REDACTED]

[REDACTED]

[REDACTED]

[REDACTED]

[REDACTED]

[REDACTED]

[REDACTED]

[REDACTED]

[REDACTED]

[REDACTED]

[REDACTED]

[REDACTED]

[REDACTED]

[REDACTED]

[REDACTED]

[REDACTED]

**9.7.9 Interim Analysis**

No interim analysis is planned for this study.

### **9.7.10 Determination of Sample Size**

The sample size and power calculations are based on the analysis of time to relapse during the 52 weeks of the DBTP. Assuming a relapse rate of 19% per 26 weeks in the placebo group and a dropout rate of 20% per 26 weeks in all treatment groups, the sample size of 200 per group will have 90% power to detect a hazard ratio of 0.475 for a rapastinel treatment versus placebo at a 0.05 significance level. To achieve this number of randomized patients, approximately 1400 patients need to be enrolled in this study if 50% of patients are qualified for randomization.

### **9.7.11 Statistical Software**

Statistical analyses will be performed using version 9.3 (or newer) of SAS.

## **9.8 DATA AND SAFETY MONITORING BOARD**

The study will be conducted under the supervision of an independent DSMB to be chartered to review safety data at predetermined points during the study. The DSMB may also decide to meet and review safety data at other time points should it be deemed necessary. The DSMB is responsible for the ongoing review of safety data in the clinical study and for making recommendations concerning the continuation, modification, and termination of the study ([FDA Guidance for Clinical Trial Sponsors: Establishment and Operation of Clinical Trial Data Monitoring Committees, March 2006](#); [European Medicines Agency Guideline on Data Monitoring Committees, EMEA/CHMP/EWP/5872/03, July 2005](#)).

All analyses that are required to support the DSMB will be performed by independent statistician(s) not otherwise involved in the study. Details of the DSMB membership, meeting schedule, and data review and analysis will be documented in the DSMB Charter.

## **9.9 CHANGES IN THE CONDUCT OF THE STUDY OR PLANNED ANALYSES**

Any amendment to this protocol will be provided to the investigator in writing by the sponsor. No protocol amendment may be implemented (with the exceptions noted below) before it has been approved by the IRB/EC and other applicable oversight bodies and the signature page, signed by the investigator, and has been received by the sponsor. If the protocol is amended to eliminate or reduce the risk to patients, the amendment may be implemented before IRB/EC review and approval in jurisdictions where regulatory authorities allow such implementation. However, the IRB/EC must be informed in writing of such an amendment, and approval must be obtained within reasonable time limits.

If unclarities arise with regard to interpretation or conduct of the approved protocol during the conduct of the study, the sponsor will provide guidance in the form of a protocol clarification letter. Such guidance will be used to clarify only within the bounds of the approved protocol.

## **9.10                      PROTOCOL DEVIATIONS**

*A protocol deviation* is any change, divergence, or departure from the study design or procedures that is under the investigator's responsibility and oversight (as defined by regulations) without prior written IRB/EC approval or favorable opinion of an appropriate amendment and that does not have a major impact on the patient's rights, safety, or well-being, or on the integrity and authenticity of the study data. Deviations may include, but are not limited to, departure from inclusion/exclusion criteria, dosing, duration of treatment, failure to perform the required assessments at specified time points, scheduling of visits not in accordance with specifications, or patient safety. Deviating from the protocol is permitted only if absolutely necessary for the safety or clinical management of the patients and must immediately be reported to the sponsor.

*A significant protocol deviation* is a form of protocol deviation that has a major impact on the patient's rights, safety, or well-being, or on the integrity and authenticity of the study data. The IRB/EC must be notified within the time period dictated by the IRB/EC associated with this study.

**10.0**                    **STUDY SPONSORSHIP**

This study is sponsored by Naurex, Inc., an indirect subsidiary of Allergan, plc.

**10.1**                    **STUDY TERMINATION**

The sponsor reserves the right to terminate the study in its entirety or at a specific study center before study completion.

**10.2**                    **REPORTING AND PUBLICATION**

All data generated in this study are the property of the sponsor. An integrated clinical and statistical report will be prepared at the completion of the study.

Publication of the results by the investigator will be subject to mutual agreement between the investigator and the sponsor and will follow the sponsor's Standard Operating Procedure on publications.

## **11.0**                    **INVESTIGATOR OBLIGATIONS**

### **11.1**                    **DOCUMENTATION**

The following must be in place and filed with the sponsor before the start of the study at each study center:

- A completed and signed Form FDA 1572 (for investigators in the US) or Investigator's Information & Agreement in lieu of FDA 1572 (for investigators outside the US). If, during the course of the study, any changes are made that are not reflected on Form FDA 1572 or Investigator's Information & Agreement in lieu of FDA 1572, a new Form FDA 1572 or Investigator's Information & Agreement in lieu of FDA 1572 must be completed and returned to the sponsor
- A fully executed contract
- The curricula vitae for the investigator and all subinvestigators listed on Form FDA 1572 or Investigator's Information & Agreement in lieu of FDA 1572, including a copy of each physician's license
- A copy of the original IRB/EC approval for conducting the study. If the study is ongoing, renewals must be submitted at yearly intervals. All subsequent modifications must be submitted and approved by the IRB/EC, as stated in Section 5.1.
- A copy of the IRB/EC-approved ICF
- A copy of the HIPAA authorization form, or other applicable local privacy forms
- A list of the IRB/EC members or the US Department of Health and Human Services general assurance number
- A copy of the laboratory certifications and reference ranges
- The investigator's Statement page in this protocol signed and dated by the investigator
- Investigators and subinvestigators will provide the sponsor with sufficient, accurate financial information as requested to allow the sponsor to submit complete and accurate financial certification or disclosure statements to the appropriate regulatory authorities. Investigators are responsible for providing information on financial interests during the course of the study and for 1 year after completion of the study.

## **11.2 PERFORMANCE**

The investigator must demonstrate reasonable efforts to obtain qualified patients for the study.

## **11.3 USE OF INVESTIGATIONAL MATERIALS**

The investigator will acknowledge that the IP supplies are investigational and as such must be used strictly in accordance with the protocol and only under the supervision of the investigator or subinvestigators listed on Form FDA 1572 (or equivalent). The IP must be stored in a secured place and must be locked. At study initiation, a representative from the sponsor will inventory the IP at the study center. The investigator must maintain adequate records documenting the receipt and disposition of all study supplies. The sponsor will supply forms on which to record the date the IP was received and a dispensing record in which to record each patient's use. All unused IP must be returned to the sponsor.

## **11.4 CASE REPORT FORMS**

All patient data relating to the study will be recorded on eCRFs to be provided by the sponsor through the EDC system. The investigator is responsible for verifying that all data entries in the eCRFs are accurate and correct by electronically signing the completed eCRF casebook submitted to the sponsor. The investigator must maintain and retain accurate documentation that supports the information entered into the EDC system for source document verification and possible regulatory inspection.

## **11.5 RETENTION AND REVIEW OF RECORDS**

Records and documents pertaining to the conduct of this study, including eCRFs, source documents, consent forms, regulatory documents, clinical laboratory results, calibration logs, or reports (including, but not limited to, all local and central laboratory results and ECG reports), and medication inventory records in all formats (including, but not limited to, written, electronic, magnetic, and optical records, and scans, x-rays, and ECGs) must be retained by the investigator for a period of at least 15 years after study completion unless local regulations or institutional policies require a longer retention period or otherwise notified in writing by the sponsor.

No study records shall be destroyed without notifying the sponsor and providing the sponsor the opportunity to arrange long-term storage for such study records or authorizing in writing the destruction of records after the required retention period.

The investigator must permit access to any documentation relating to the study upon request of the sponsor or applicable regulatory authorities. If the investigator for the study retires, relocates, or for other reasons withdraws from the responsibility of keeping the study records, custody must be transferred to a suitable alternate custodian employee of the institution or to a suitably qualified and responsible third party. The sponsor must be notified in writing of the name and address of the new custodian in advance of the transfer.

## **11.6 PATIENT CONFIDENTIALITY**

- Participants will be assigned a unique identifier (PID). Any participant records or datasets that are transferred to the sponsor will contain the identifier only; participant names or any information which would make the participant identifiable will not be transferred.
- The participant must be informed that his/her personal study-related data will be used by the sponsor in accordance with local data protection law. The level of disclosure must also be explained to the participant.
- The participant must be informed that his/her medical records may be examined by Clinical Quality Assurance auditors or other authorized personnel appointed by the sponsor, by appropriate IRB/IEC members, and by inspectors from regulatory authorities.

**APPENDIX IV. SCALES AND QUESTIONNAIRES**

Please refer to the Study Reference Manual for reference copies of scales and questionnaires.

# 2.0 INTRODUCTION

This Statistical Analysis Plan (SAP) describes the methodology that will be used to summarize the statistical analyses of the efficacy and safety data for the final protocol of Study RAP-MD-33 (version dated 02MAY2018).

Study RAP-MD-33 is a Phase 3, multicenter, randomized-withdrawal, parallel-group, placebo-controlled, maintenance study to evaluate the efficacy, safety, and tolerability of rapastinel in the prevention of relapse in patients with major depressive disorder (MDD) who completed one of the rapastinel lead-in studies including RAP-MD-30 and RAP-MD-32. The RAP-MD-31 study was terminated before any patient was enrolled. Thus, there is no patient rolled-over from the RAP-MD-31 study to RAP-MD-33 study.

The study will be conducted in the following periods:

- An 8- to 16-week open-label treatment period (OLTP) where patients receive rapastinel 225 or 450 mg IV weekly
- A randomized double-blind treatment period (DBTP) of at most 52 weeks of treatment duration where patients are randomized 1:1:1 to either rapastinel 225 or 450 mg weekly, rapastinel clinically driven schedule (IV, 225 or 450 mg, variable interval, placebo on intervening weeks) or placebo
- A 2-week safety follow-up period

In order for patients to transition from the OLTP and be randomized into the DBTP, the patient must meet the stability criterion sometime after 8 weeks (and up to 16 weeks) during the OLTP. A patient will be considered a stable responder upon achieving both criteria (1) and (2) below:

- 1) An observed Montgomery-Asberg Depression Rating Scale (MADRS) total score  $\leq 12$  with no more than one modest MADRS excursion (MADRS total score > 12 but  $\leq 16$ ) for at least six consecutive weeks.
- 2) An observed MADRS total score  $\leq 12$  for at least two consecutive visits prior to randomization.

The OLTP starts with the first dose of open-label treatment and ends with one of the following: the first dose of double-blind treatment for patients who enter the DBTP or Visit 69/Week 52 End-of-Treatment/Early Termination (ET) assessments for patients who do not enter the DBTP.

The double-blind treatment period starts when the first dose of double-blind treatment is administered and ends when the patient meets relapse criteria, completes 52 weeks of double-blind treatment, or discontinues for other reasons.

The safety follow-up (SFU) period starts after completion of the last scheduled assessment (or ET) and ends with the last available assessment.

Individual treatment durations will vary. The maximum duration of the study will be 70 weeks.

RAP-MD-33 Statistical Analysis Plan

RAP-MD-33 Statistical Analysis Plan

Page 10

Page 12

RAP-MD-33 Statistical Analysis Plan

Page 13

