#### *9.5.2.1.4 Reporting Adverse Events and Serious Adverse Events*

At each visit, patients are to be queried regarding any AEs or SAEs that have occurred since the previous visit. Patients will be asked to volunteer information with a nonleading question such as, “How do you feel since your last visit?” Study center personnel will record all pertinent information in the patient’s eCRF.

All AEs must be recorded on the appropriate AE reporting page of the patient’s eCRF whether or not they are considered causally related to the IP.

For every AE, the investigator must:

- Provide an assessment of the seriousness of the event (ie, is it an SAE?), as well as the severity and casual relationship
- Document all actions taken with regard to the IP
- Detail any other treatment measures taken for the AE
- Document the outcome of the AE

In addition, patients are to be reminded, as described in the ICF and in accordance with Section 9.5.2.1, to notify study center personnel of any AEs occurring during the 30-day poststudy period. Any AEs reported by the patient (or patient representative) during this period are to be recorded in original source documents. AEs are also to be recorded in the eCRF if at least one of the following conditions is met: 1) the event meets the criteria for an SAE (see Sections 9.5.2.1.3 and 9.5.2.1.4), and/or 2) the event is judged by the investigator to be potentially causally related to IP (Section 9.5.2.1.1).

Any AEs that are ongoing at the time of the final protocol-defined study visit will be followed until the condition returns to prestudy status, has resolved or stabilized, or can be explained as being unrelated to the IP. If a follow-up visit is deemed necessary for appropriate safety surveillance, it will take place within 30 days of the final protocol-defined study visit.

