## 9.1 ADVERSE EVENTS

AEs will be coded using the Medical Dictionary for Regulatory Activities.

An AE (classified by preferred term) that occurs during the OLTP or thereafter will be considered a treatment-emergent adverse event (TEAE) if it was not present before the date of the first dose of IP in the lead-in study or was present before the first dose of IP in the lead-in study and increased in severity during the OLTP or thereafter. An AE that becomes serious during the OLTP or thereafter will also be considered as TEAE. If more than 1 AE is reported before the date of the first dose of IP in the lead-in study and coded to the same preferred term, the AE with the greatest severity will be used as the benchmark for comparison with the AEs occurring during the OLTP or thereafter that were also coded to that preferred term. An AE that occurs more than 30 days after the date of the last dose of IP will not be counted as a TEAE.

An AE (classified by preferred term) that occurs during the OLTP of the study will be considered a newly emergent adverse event (NEAE) if the AE was not present before the first dose of IP in the OLTP or it was present before the first dose of IP in the OLTP and increased in severity during the OLTP. An AE that becomes serious during the OLTP will also be considered as NEAE. If more than 1 AE is reported before the first dose of IP in the OLTP and coded to the same preferred term, the AE with the greatest severity will be used as the benchmark for comparison with the AEs occurring during the OLTP that were also coded to that preferred term.

An AE (classified by preferred term) that occurs during the DBTP of the study will be considered a newly emergent adverse event (NEAE) if the AE was not present before the first dose of IP in the DBTP or it was present before the first dose of IP in the DBTP and increased in severity during the DBTP. An AE that becomes serious during the DBTP will also be considered as NEAE. If more than 1 AE is reported before the first dose of IP in the DBTP and coded to the same preferred term, the AE with the greatest severity will be used as the benchmark for comparison with the AEs occurring during the DBTP that were also coded to that preferred term.

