An AE (classified by preferred term) that occurs during the SFU of the study will be considered a newly emergent adverse event (NEAE) if the AE was not present before or at Visit 70 or it was present before or at Visit 70 and increased in severity during the SFU. An AE that becomes serious during the SFU will also be considered as NEAE. If more than 1 AE is reported before or at Visit 70 and coded to the same preferred term, the AE with the greatest severity will be used as the benchmark for comparison with the AEs occurring during the SFU that were also coded to that preferred term.

An AE that occurs more than 30 days after the date of the last dose of IP will not be counted as an NEAE.

An SAE that occurred between the date of the first dose of IP in the OLTP and 30 days after the date of the last dose of IP, inclusive, will be considered a treatment-emergent SAE (e.g., TESAE).

The overall number and percentage of patients with TEAEs, NEAEs, death, TESAEs, TEAEs leading to study discontinuation and TEAEs related to study drug during the OLTP will be tabulated overall, and during the DBTP and the SFU by treatment group.

The incidence of common ( $\geq 2\%$  of patients in any treatment group) TEAEs and NEAEs during the OLTP will be summarized overall by preferred term. Similarly, the incidence of common TEAEs and NEAEs during the DBTP and during the SFU will be summarized by preferred term and treatment group and will be sorted by decreasing frequency starting with the weekly rapastinel group followed by the clinically driven schedule rapastinel group.

Listings will be presented for all patients with AEs and patients who died (if any).

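### SAP 9.1 counts adverse events to 30 days after the last dose but tabulates them only in periods that end at the last assessment, and its Visit 70 benchmark contradicts that period

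*SAP*

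**What the plan says.** **Counting window (SAP 9.1).** TEAEs: "An AE that occurs more than 30 days after the date of the last dose of IP will not be counted as a TEAE". NEAEs: "An AE that occurs more than 30 days after the date of the last dose of IP will not be counted as an NEAE". Serious events from the first OLTP dose to "30 days after the date of the last dose of IP, inclusive, will be considered a treatment-emergent SAE".

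**Tables (SAP 9.1).** The overall table of TEAEs, NEAEs, deaths and TESAEs gives events "during the OLTP will be tabulated overall, and during the DBTP and the SFU by treatment group". For common events, "the incidence of common TEAEs and NEAEs during the DBTP and during the SFU will be summarized by preferred term and treatment group", with the OLTP handled in the sentence before.

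**Period limits.** SAP 2.0 says the DBTP "ends when the patient meets relapse criteria, completes 52 weeks of double-blind treatment, or discontinues for other reasons", and then: "The safety follow-up (SFU) period starts after completion of the last scheduled assessment (or ET) and ends with the last available assessment". Both documents plan a 2-week follow-up. SAP 14.2 schedules one follow-up visit, Visit 70 at Week 54 (Day 378), places it within the follow-up phase, and closes the DBTP window at Visit 69.

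**NEAE benchmark in follow-up (SAP 9.1).** A follow-up NEAE must be absent up to and including Visit 70, or must worsen or become serious during follow-up.

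**Collection (Protocol 9.5.2.1 and 9.5.2.1.4).** AEs are collected until 30 days after the final visit. Patients are reminded "to notify study center personnel of any AEs occurring during the 30-day poststudy period". From that stretch, only serious or possibly IP-related events are entered in the eCRF.

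**The concern.** The counting window and the tabulation periods have different ends. An event can meet the SAP's definition of treatment-emergent and yet occur after the last period that any described table covers. The events concerned are not trivial: after the final visit the eCRF receives only serious or possibly related ones. In a withdrawal trial in depression, a serious event about three weeks after the last dose should not depend on a programmer's choice for whether it is counted.

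Protocol 9.7.6.1 planned SAE summaries by preferred term. SAP 15.0 limits output to what an abbreviated report needs, and in the released SAP text the overall table is the only one that counts TESAEs. No other table described there would recover a missed event.

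The Visit 70 benchmark adds a second difficulty. It looks as if the follow-up period were meant to begin at Visit 70, whereas SAP 2.0 begins it after Visit 69/ET.

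**Working it through.** **1. Reproduce the plan's own figures.** Maximum duration = 16 weeks OLTP + 52 weeks DBTP + 2 weeks follow-up = 70 weeks, as SAP 2.0 states. Visit 70 = 54 × 7 = Day 378 and Visit 69 = 52 × 7 = Day 364, as in SAP 14.2. The follow-up visit is therefore 378 − 364 = 14 days after Visit 69.

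**2. Day of the last dose.** Dosing is weekly for up to 52 weeks. The documents do not say whether a dose is given at Visit 69, so both cases are taken: Day 364 (Week 52) and 51 × 7 = Day 357 (Week 51).

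**3. Days in the counting window but in no period.** Uncovered days = (last dose day + 30) − day of last assessment.

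| Last dose | Window ends | Last assessment | Uncovered days | Share of 30 days |
|---|---|---|---|---|
| Day 364 | Day 394 | Day 378 | 16 | 53% |
| Day 357 | Day 387 | Day 378 | 9 | 30% |

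The shares are of calendar days, not of events.

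**4. Other timings.** With the last assessment 0, 7, 14, 21 or 30 days after the last dose, the uncovered part is 30, 23, 16, 9 or 0 days. The gap closes only if an assessment takes place 30 or more days after the last dose.

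**5. The Visit 70 benchmark beside the SAP 2.0 period.** Take a patient whose last assessment is Visit 70.

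- An event that starts between ET and Visit 70 lies inside follow-up, but it was present by Visit 70. Read literally, it cannot be a follow-up NEAE unless it later worsens or becomes serious.
- An event that starts after Visit 70 meets the NEAE wording, but follow-up ended at Visit 70.

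A new event therefore fails one condition or the other. The benchmark, the end of follow-up and the 30-day window cannot all be applied as written.

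**6. Patients who never enter the DBTP.** Protocol 9.1.1 sends patients who discontinue from the OLTP to the same follow-up. SAP 9.1 tabulates follow-up by treatment group, and these patients have no double-blind group, so their follow-up events have no column.

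**The case against.** **SAP 9.1 already assigns late events to follow-up.** Its Visit 70 benchmark implies a follow-up period that continues after Visit 70. This is the best argument against the gap, and it shows what the authors may have intended. But it concerns NEAEs only, it contradicts SAP 2.0, and it excludes new events between ET and Visit 70. It turns part of the gap into a contradiction and does not resolve it.

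**Extra visits.** Protocol 9.1.3 allows further follow-up visits within 30 days for safety reasons, and a serious event is a likely cause of one. Such a visit extends follow-up. This stands: 9 to 16 days is the figure for patients without a later visit.

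**Listings.** AE and death listings are not limited by period, so late events remain visible. This stands, but a listing gives no count or percentage by arm.

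**Unseen text.** The contents page of the SAP lists a section 14.3 on derived variables whose heading is absent from the released text. Period flags could be defined there. The conclusion rests on the rules that can be read.

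**A stronger reading: a lost week at relapse.** A reader might infer that about a week is lost for each MADRS-defined relapser, because section 14 of the SAP dates such a relapse at the first of two visits, and that this falls more heavily on placebo. The documents do not support it. The criterion needs two consecutive visits and cannot be met before the second. The back-dating defines the relapse date for the efficacy endpoint; nothing makes it an AE period boundary. Protocol 9.1.2 calls for the Visit 69/ET procedures once criteria are met, and SAP 14.2 ends the DBTP window at Visit 69. What remains is narrow: a relapse dated between visits from the CRF, such as a hospitalization, where SAP 2.0 read literally leaves the days up to ET in neither period. The documents give no basis for sizing this.

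**Conclusion.** The mismatch is real on the SAP's stated rules. For a patient who completes on schedule with no later visit, the last 9 to 16 days of the 30-day window lie in no tabulated period, depending on whether the last dose is at Week 52 or Week 51. With no assessment after the last dose it would be all 30 days. Separately, the Visit 70 benchmark is incompatible with the follow-up period as SAP 2.0 defines it.

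The effect is on counts and percentages in descriptive tables, not on data capture or listings. The number of events affected cannot be derived from the documents and is probably small. No claim of a bias between arms follows. The point is still worth correcting, because the rules as written would change the TEAE and TESAE counts reported, and the late events that reach the database are serious or possibly related ones.

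**What to change.** For AE tabulation only, amend SAP 2.0 and 9.1 as follows.

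1. End the DBTP at the Visit 69/ET date, as the SAP 14.2 window already does. This also covers relapses dated between visits.
2. Run follow-up from after ET to the later of the last follow-up assessment and 30 days after the last dose of IP. The existing 30-day limit on TEAEs, NEAEs and TESAEs stays. For a patient followed to Visit 70, uncovered days fall from 9–16 to 0.
3. Change the follow-up NEAE benchmark from Visit 70 to the Visit 69/ET assessment, so that new events after ET can qualify.
4. Show post-ET events of patients who never entered the DBTP in a separate column, since they have no double-blind treatment group.

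The cost is a few sentences and minor reprogramming. No new data are needed, and the efficacy relapse date is unaffected. Reported counts may rise slightly.
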